**Statistical Analyses Statistical Methods/Analyses**

The baseline value, unless otherwise specified, will be defined as the most recent non-missing measurement collected before the first dose of study drug in the Treatment Period (i.e., the Day 1 Visit). The TEZ/IVA Run-in Period is intended to establish a reliable on-treatment (TEZ/IVA) baseline for comparison during the Treatment Period.

The primary efficacy endpoint is the absolute change in CFQ-R respiratory domain score from baseline through Week 24. The primary null hypothesis to be tested is that the mean absolute change in CFQ-R respiratory domain score from baseline through Week 24 is the same for the VX-445/TEZ/IVA and TEZ/IVA groups. The null hypothesis will be tested at a 2-sided significance level of 0.05.

Assuming a within-group SD of 18 and a treatment difference of 10 between VX-445/TEZ/IVA and TEZ/IVA, a sample size of 71 subjects completing the Treatment Period in each group for a total of 142 subjects will have approximately 90% power for the CFQ-R respiratory domain score hypothesis testing, based on a 2-sample t-test at a significance level of 0.05. Assuming a 10% dropout rate, up to approximately 158 subjects will be enrolled.

The primary analysis for CFQ-R will be based on a mixed-effects model for repeated measures (MMRM). The primary result obtained from the model will be the estimated treatment difference through Week 24. The treatment difference at each post-baseline visit, obtained from the model, will also be provided.

A hierarchical fixed-sequence testing procedure will be used to control the overall family-wise type I error for the testing of the primary endpoint and key secondary endpoint.

The safety endpoints include AEs, clinical laboratory values, ECGs, vital signs, and pulse oximetry through the Safety Follow-up Visit. The safety analysis will be descriptive only.

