**Table 3-2 Study VX18-445-109: Treatment Period and Safety Follow-up Visit**

Event/ Assessment a	TEZ/IVA Run-in Period (4 weeks)		Treatment Period (24 weeks)								ETT Visit b	Safety Follow-up Visit c (28 ± 7 Days After Last Dose of Study Drug)	Comments
	Day -28 ± 1 day	Day -14 (Day -15 to Day -3)	Day 1 d	Day 15 ± 3 days	Week 4 ± 5 days	Week 8 ± 5 days	Week 12 ± 5 days	Week 16 ± 5 days	Week 20 ± 5 days	Week 24 ± 5 days			
Clinic visit	X	X	X	X	X	X		X		X	X	X	
Telephone contact							X		X				Assess the subject's status, any AEs, concomitant medications, treatments, and procedures.
Inclusion and exclusion criteria confirmation	X												
CFQ-R			X		X	X		X		X	X	X	Completed before any other assessments scheduled at relevant visits (Section 11.4.1).
Weight and height	X		X	X	X	X		X		X	X	X	Measured with shoes off. Height will only be collected for subjects ≤21 years of age on the date of informed consent (Section 11.4.3).
Ophthalmologic examination										X	X		Subjects <18 years of age on the date of informed consent and who completed at least 12 weeks of study drug treatment will have a single ophthalmologic examination at either the ETT or Week 24 Visit, whichever comes first (Section 11.5.6).
Complete physical examination	X		X		X					X	X		Symptom directed physical examinations may be performed at any time if deemed necessary by the investigator (Section 11.5.3).

a All assessments will be performed before dosing unless noted otherwise.

b If a subject prematurely discontinues study drug treatment, an ETT Visit should be scheduled as soon as possible after the decision to discontinue treatment. Subjects who prematurely discontinue treatment during the Treatment Period will continue to complete all scheduled study visits for assessments following completion of the ETT Visit.

c The Safety Follow-up Visit is required for all subjects, unless the subject completes the Week 24 Visit and has enrolled in a separate open-label study within 28 days after the last dose of study drug. If an ETT Visit occurs 3 weeks or later following the last dose of study drug, then the ETT Visit replaces the Safety Follow-up Visit.

d To enter the Treatment Period, conditions for entry must be satisfied.

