## 12.3 Statistical Analysis

### 12.3.1 General Considerations

**Continuous variables** will be summarized using the following descriptive summary statistics: the number of subjects (n), mean, SD, median, minimum value (min), and maximum value (max).

**Categorical variables** will be summarized using counts and percentages.

The **baseline value**, unless otherwise specified, will be defined as the most recent non-missing measurement (scheduled or unscheduled) collected before the first dose of study drug in the Treatment Period (i.e., the Day 1 Visit). For ECG, baseline will be defined as the most recent pretreatment measurement (or the average of triplicate measurements, if the most recent pretreatment measurement is obtained in triplicate) before the first dose of study drug in the Treatment Period (i.e., the Day 1 Visit).

**Absolute change** from baseline will be calculated as post-baseline value – baseline value.

The **Treatment-emergent (TE) Period for the Run-in Period** will be from the first dose of study drug in the Run-in Period to (1) the first dose of study drug in the Treatment Period for subjects who complete the Run-in Period and continue to the Treatment Period, or (2) 28 days

after the last dose date of study drug in the Run-in Period for subjects who do not continue to the Treatment Period (e.g., subjects who do not meet the conditions to enter the Treatment Period).

The **TE Period for the Treatment Period** will include the time from the first dose date of study drug in the Treatment Period (VX-445/TEZ/IVA or placebo + TEZ/IVA) to 28 days after the last dose of the study drug or to the completion of study participation date (as defined in Section 9.1.7), whichever occurs first.

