### 12.3.4 Safety Analysis

All safety analyses will be based on data from the TE Period for all subjects in the Safety Set. The overall safety profile of study drug will be assessed based on the following safety and tolerability endpoints:

- Treatment-emergent adverse events (TEAEs)
- Clinical laboratory values (i.e., hematology, serum chemistry, coagulation, and urinalysis)
- ECGs
- Vital signs
- Pulse oximetry

All safety data from the TE Period will be summarized by treatment group, unless otherwise specified.

All safety data will be presented in individual subject data listings, including safety data from the Run-in Period.

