9 STATISTICAL ANALYSIS

9.1 General Considerations

Continuous variables will be summarized using the following descriptive summary statistics: the number of subjects (n), mean, SD, median, minimum value (min), and maximum value (max).

Categorical variables will be summarized using counts and percentages.

Baseline value, unless otherwise specified, will be defined as the most recent non-missing measurement (scheduled or unscheduled) collected before the first dose of study drug in the Treatment Period (i.e., the Day 1 Visit). For ECG, baseline will be defined as the most recent pretreatment measurement (or the average of triplicate measurements, if the most recent pretreatment measurement is obtained in triplicate) before the first dose of study drug in the Treatment Period (i.e., the Day 1 Visit).

Absolute change from baseline will be calculated as post-baseline value – baseline value.

Relative change from baseline will be calculated as (post-baseline value – baseline value)/baseline value.

The **Treatment-emergent (TE) Period for the Run-in Period** will be from the first dose of study drug in the Run-in Period to (1) the first dose of study drug in the Treatment Period for subjects who complete the Run-in Period and continue to the Treatment Period, or (2) 28 days after the last dose date of study drug in the Run-in Period or date of completion of study participation, whichever occurs first, for subjects who do not continue to the Treatment Period (e.g., subjects who do not meet the conditions to enter the Treatment Period).

The **TE Period for the Treatment Period** will include the time from the first dose date of study drug in the Treatment Period (ELX/TEZ/IVA or placebo + TEZ/IVA) to 28 days after the last dose of the study drug or to the date of completion of study participation, whichever occurs first.

Unscheduled visits: Unscheduled visit measurements will be included in analysis as follows:

- 1) In scheduled visit windows per specified visit windowing rules
- 2) In the derivation of baseline and last on-treatment measurements
- 3) In the derivation of maximum and minimum values during TE period, and maximum and minimum change from baseline values during TE period for safety analyses
- 4) In individual subject data listings as appropriate

Visit windowing rules: The analysis visit windows for protocol-defined visits are provided in [Appendix A](#).

Incomplete/missing data will not be imputed, unless specified otherwise.

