9.4 Safety Analysis

All safety analyses will be based on data from the TE period for the Treatment Period and based on the Safety Set for the Treatment Period, unless otherwise specified. Subjects will be analyzed according to the treatment they actually received in the Treatment Period. For subjects receiving study drug from more than one treatment group, the treatment group allocation will be the higher treatment group (ELX/TEZ/IVA > TEZ/IVA).

The overall safety profile of study drug will be assessed in terms of the following safety and tolerability endpoints:

- Treatment-emergent adverse events (TEAEs)
- Clinical laboratory values
- ECGs
- Vital signs
- Pulse oximetry

Only descriptive analysis of safety will be performed and no statistical testing will be performed.

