12 LIST OF APPENDICES

Appendix A: Analysis Visit Windows for Safety and Efficacy Assessment

Table 12-1 Analysis Visit Windows for Safety and Efficacy Assessments			
Assessment	Visit¹	Target Study Day	Analysis Visit Window (in study days)^{2,3,4,5}
Safety Assessment			
Serum Chemistry Hematology	Day 1 (Baseline)	1	≤1 Pre-dose
	Day 15	15	[1, 22]
	Week 4	29	(22, 43]
	Week 8	57	(43, 85]
	Week 16	113	(85, 141]
	Week 24	169	(141, 183]
	Safety Follow-up	Not applicable	Use nominal visit
Standard 12-lead ECG	Day 1 (Baseline)	1	≤1 Pre-dose
	Week 8	57	[1, 113]
	Week 24	169	(113, 183]
	Safety Follow-up	Not applicable	Use nominal visit
Vital signs and pulse oximetry (excluding BMI, Weight, Height and their Z-scores)	Day 1 (Baseline)	1	≤1
	Day 15	15	[1, 22]
	Week 4	29	(22, 43]
	Week 8	57	(43, 85]
	Week 16	113	(85, 141]
	Week 24	169	(141, 183]
	Safety Follow-up	Not applicable	Use nominal visit
Coagulation	Day 1 (Baseline)	1	≤1 Pre-dose
	Week 24	169	[1, 183]
	Safety Follow-up	Not applicable	Use nominal visit
BMI, Weight, Height and their Z-scores	Day 1 (Baseline)	1	≤1
	Day 15	15	(1, 22]
	Week 4	29	(22, 43]
	Week 8	57	(43, 85]
	Week 16	113	(85, 141]
	Week 24	169	(141, 183]
	Safety Follow-up	Not applicable	>183
Efficacy Assessment and Pharmacodynamic Assessment			
Spirometry	Day 1 (Baseline)	1	≤1 Pre-dose
	Day 15	15	(1, 22]
	Week 4	29	(22, 43]
	Week 8	57	(43, 85]
	Week 16	113	(85, 141]
	Week 24	169	(141, 183]
	Safety Follow-up	Not applicable	>183
Sweat Chloride	Day 1 (Baseline)	1	≤1 Pre-dose
	Week 4	29	(1, 43]
	Week 8	57	(43, 113]
	Week 24	169	(113, 183]

Table 12-1 Analysis Visit Windows for Safety and Efficacy Assessments			
Assessment	Visit¹	Target Study Day	Analysis Visit Window (in study days)^{2, 3, 4, 5}
CFQ-R	Day 1 (Baseline)	1	≤1
	Week 4	29	(1, 43]
	Week 8	57	(43, 85]
	Week 16	113	(85, 141]
	Week 24	169	(141, 183]
	Safety Follow-up	Not applicable	>183

Notes:

¹ Visit name for analysis purpose is used to report data in tables and figures.

² The analysis visit windows will be applied using the following rules for both scheduled and unscheduled visits:

- If no numerical measurement is available within a visit window, the measurement will be considered missing for the visit.
- If there is more than 1 numerical measurement available within a visit window, use the following rules:
 - The measurement closest to the target day will be used; or
 - If there are multiple measurements with the same distance from the target day, the latest measurement will be used.

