³ For lab, ECG and vital sign measurement collected on the date of first dose of study drug, if it cannot be determined whether the measurement is before or after the first dose:

- Scheduled measurement will be treated as pre-dose observation.
- Unscheduled measurement will be treated as post-dose observation.

⁴ For safety assessment, Safety Follow-up analysis visit will be based on nominal Safety Follow-up visit. If a subject doesn't have a nominal Safety Follow-up visit but has an ETT visit with study day >183, then the ETT visit will be mapped into Safety Follow-up analysis visit.

⁵ For efficacy assessments and nutrition variables (BMI, Weight, Height and their Z-scores), if there are multiple assessments >183, then nominal Safety Follow-up visit will be mapped to Safety Follow-up visit. If there is only ETT assessment > 183, the ETT visit will be mapped to the Safety Follow-up visit; else if there are multiple assessments with >183 then select the earliest record.

Derived Variables:

- Age (in years) at first dose date and nominal visit (for demographics, listing and the calculation of [percent] predicted spirometry variables):

Obtain the age at informed consent (in days) in “yy, mm” format (e.g., 24 years, 6 months) from the Vital Signs (VS) page at the Screening Visit, and add 0.5 month to convert to days.

Obtain the informed consent date.

Then age (in years) at first dose or nominal visit = [(first dose date or nominal visit date – informed consent date) in days + age at informed consent (in days)]/365.25.
- Age (in months) at nominal visit (for use in calculation of BMI and weight z-score):

Obtain the age at informed consent (in months) in “yy, mm” format (e.g., 24 years, 6 months) from Vital Signs (VS) page at the Screening Visit.

Obtain the informed consent date.

Then age (in months) at nominal visit = integer part of {(age at informed consent (in months) + 0.5 + diff(first dose date or nominal visit date, informed consent date) in months)} + 0.5.
- Missing first dose date or last dose date

Table 12-1 Analysis Visit Windows for Safety and Efficacy Assessments			
Assessment	Visit¹	Target Study Day	Analysis Visit Window (in study days)^{2, 3, 4, 5}

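### Should the treatment-emergent period be extended to cover Safety Follow-up Visits held on days 29 to 35 after the last dose?

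*SAP*

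**What the plan says.** - **End of the TE period.** SAP 9.1 runs it from the first randomized dose "to 28 days after the last dose of the study drug or to the date of completion of study participation, whichever occurs first". Protocol 12.3.1 has the same rule: "to 28 days after the last dose of the study drug or to the completion of study participation date", if that comes first.
- **Visit window.** Protocol Table 3-2 places the Safety Follow-up Visit at "28 ± 7 Days After Last Dose of Study Drug".
- **Data used.** Protocol 12.3.4: "All safety analyses will be based on data from the TE Period for all subjects in the Safety Set". SAP 9.4: "All safety analyses will be based on data from the TE period for the Treatment Period", with an allowance for exceptions specified elsewhere.
- **Synopsis.** "The safety endpoints include AEs, clinical laboratory values, ECGs, vital signs, and pulse oximetry through the Safety Follow-up Visit".
- **Reporting visits.** SAP Appendix A, note 4: "For safety assessment, Safety Follow-up analysis visit will be based on nominal Safety Follow-up visit". Note 1 gives the purpose: "Visit name for analysis purpose is used to report data in tables and figures". Neither note sets a day-28 limit.

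**The concern.** Two subjects could both keep to the schedule and be counted differently. A raised transaminase at a follow-up visit on day 27 enters the threshold table, while the same value on day 30 does not. A rash that begins on day 30 is a post-treatment event and is missing from the TEAE and special-interest tables. This appears to contradict the synopsis.

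It also seems to fall on a group of interest. Week 24 completers who roll over within 28 days of the last dose need no Safety Follow-up Visit (Protocol 9.1.4), so those who have one are mainly early stoppers and completers who do not roll over. The natural remedy would be to end the TE period at the later of day 28 and the Safety Follow-up Visit, up to day 35 and not beyond completion of participation.

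**Working it through.** **1. Days outside the TE period.** Window = 28 − 7 to 28 + 7 = days 21 to 35, which is 15 days. Days after 28 are 29 to 35, which is 7 days. 7/15 = 46.7%.

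**2. Share of visits.** The documents give no distribution of visit days, so two shapes are assumed.
- Even spread: 46.7%.
- Triangular, centred on the day-28 target, weight 8 − |day − 28|: total 8 + 2 × (7+6+5+4+3+2+1) = 64; days 29 to 35 carry 28; 28/64 = 43.8%.

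**3. Number of subjects.** The roll-over share r is not given, so it is varied. With 158 subjects, and every subject who does not roll over attending the visit, the number is 158 × (1 − r) × share.

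| r | even spread | triangular |
|---|---|---|
| 0% | 73.7 | 69.1 |
| 50% | 36.9 | 34.6 |
| 90% | 7.4 | 6.9 |
| 100% | 0 | 0 |

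These are subjects with a visit after day 28, not subjects with a lost safety finding.

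**4. What is excluded.**
- *Adverse events.* SAP 9.4.1 classifies an event by when it developed or worsened, not by when it was recorded. An event starting on day 25 and first reported on day 33 is a TEAE. Only onset or worsening after day 28 is excluded.
- *Threshold and shift tables.* The laboratory, ECG and vital sign threshold tables and the oximetry shift table (SAP 9.4.2 to 9.4.5) are confined to the TE period, so values from days 29 to 35 are excluded.
- *By-visit tables.* These are described as summaries of treatment-emergent measurements, but Appendix A gives them a Safety Follow-up visit taken from the nominal visit. Exclusion is not established here.
- *Listings.* Nothing is dropped. SAP 9.4.1 lists all AEs, including post-treatment ones, and all SAEs and deaths with a TEAE flag. SAP 9.4.2 to 9.4.4 list laboratory, ECG and vital sign values from scheduled and unscheduled visits. Protocol 12.3.4 calls for all safety data to be listed.

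**5. Effect of the remedy.** Let v be the day of the Safety Follow-up Visit, from 21 to 35.
- *Completer who does not roll over.* Participation ends at that visit (Protocol 9.1.7). Present rule: min(28, v), so day 21 to 28, a spread of 7 days. Remedy: min(max(28, v), v) = v, so day 21 to 35, a spread of 14 days.
- *Early stopper whose Week 24 Visit falls more than 35 days after the last dose.* Present rule: day 28 for everyone. Remedy: max(28, v), so day 28 to 35.
- *Roll-over subject.* The period ends at the Week 24 Visit under either rule.

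The remedy brings all 15 permitted days inside the period, but it makes the length of observation depend more on the appointment date. Early stoppers also keep attending scheduled visits to Week 24 (Protocol 9.1.5.2), so some of their off-drug data would fall after day 35 and stay outside the TE period anyway.

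**The case for a change.** The best case for a change is that listings do not repair incidence tables. The synopsis promises coverage through the follow-up visit, and two programmers could fill the Safety Follow-up rows differently, because the SAP text says treatment-emergent while Appendix A says nominal visit. Redefining the period would need only a wording change and date-derivation code, and at most 7 more off-drug days would count, equally in both arms.

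The mismatch with the synopsis stands, and so does the silence about the follow-up rows. Neither supports a new TE definition. The synopsis line is a one-sentence statement of scope, while the operative sections of the protocol and SAP agree with each other. The follow-up rows have a sensible reading: a table row defined by nominal visit holds the values from that visit, and SAP 9.4 allows for rules specified elsewhere.

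The argument about early stoppers is weaker than it looks. They also have an Early Termination of Treatment Visit as soon as possible after the decision to stop, with chemistry, hematology, coagulation, ECG, vital signs and oximetry (Protocol 9.1.5 and Table 3-2). That visit will normally fall within 28 days of the last dose.

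**Conclusion.** No change to the plan is needed. A visit window that reaches day 35 does overrun a TE period that ends by day 28, and values or new events from days 29 to 35 are left out of the TEAE, threshold and oximetry shift tables. That is a fair trade-off. The cut-off is prespecified, set at the visit's target day, identical in both arms and consistent between Protocol 12.3.1 and SAP 9.1, and the later data remain in the listings. SAP 9.4 plans no safety testing, so no inference depends on it. Tying the cut-off to the visit date would widen its range for completers who do not roll over from 7 to 14 days.

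The synopsis sentence is a clerical looseness, and the content of the follow-up rows is a detail that analysts can settle from Appendix A.

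The figure of 44% to 47% is a share of follow-up visits, not of subjects, and rests on assumed distributions of visit days. The count of 0 to about 74 subjects rests on an unknown roll-over share. It is an upper bound on those whose tabulated safety data could be touched by a follow-up visit after day 28.

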9.2 Background Characteristics

9.2.1 Subject Disposition

A disposition table will be provided for the Run-in Period with the number of subjects in:

- All Subjects Set
- Safety Set for the Run-in Period

The number and percentage (based on Safety Set for the Run-in Period) of subjects in each of the following disposition categories will be summarized:

- Completed run-in period treatment
- Prematurely discontinued Run-in period treatment and the reason for treatment discontinuation
- Prematurely discontinued study during Run-in period and the reason for study discontinuation

A separate disposition table will be provided for the Treatment Period by treatment group and overall with the number of subjects in:

- Randomized
- Full Analysis Set
- Safety Set for the Treatment Period
- Randomized but not dosed in the Treatment Period

The number and percentage (based on FAS) of subjects in each of the following disposition categories will be summarized by treatment group and overall:

- Completed study drug treatment
- Prematurely discontinued treatment and the reason for discontinuation (i.e., discontinued all study drugs)
- Completed study
- Prematurely discontinued the study and the reason for discontinuation
- Rollover to the open-label study

A listing will be provided for subjects who discontinued treatment (including both the Run-in Period and Treatment Period) or who discontinued study with reasons for discontinuation.

9.2.2 Demographics and Baseline Characteristics

Demographics and baseline characteristics will be summarized based on the FAS, and presented by treatment group and overall.

Demographic data will include the following:

- Age at baseline (in years)
- Sex (female and male)
- Ethnicity (Hispanic or Latino, not Hispanic or Latino, and not collected per local regulations)
- Race (White, Black or African American, Asian, American Indian or Alaska Native, Native Hawaiian or Other Pacific Islander, Other, and not collected per local regulations)
- Country

Baseline characteristics will include the following:

- Weight (kg)
- Height (cm)
- BMI (kg/m²)

Stratification categories will include the following:

- Age at Screening Visit (<18, ≥18 years)
- ppFEV₁ at Day -14 (<70, ≥70)
- CFTR modulator use at the Screening Visit (Yes, No)

Disease characteristics will include the following:

- CFQ-R respiratory domain score at baseline (continuous)
- ppFEV₁ at baseline (<40, ≥ 40 to <70, ≥70 to ≤90, and >90)
- ppFEV₁ at baseline (continuous)
- Sweat chloride at baseline (continuous)
- Prior use of dornase alfa before the first dose of study drug in the Treatment Period (Yes, No)
- Prior use of azithromycin before the first dose of study drug in the Treatment Period (Yes, No)
- Prior use of inhaled antibiotic before the first dose of study drug in the Treatment Period (Yes, No)
- Prior use of bronchodilator before the first dose of study drug in the Treatment Period (Yes, No)
- Prior use of inhaled bronchodilator before the first dose of study drug in the Treatment Period (Yes, No)
- Prior use of inhaled hypertonic saline before the first dose of study drug in the Treatment Period (Yes, No)

- Prior use of inhaled corticosteroids before the first dose of study drug in the Treatment Period (Yes, No)
- Infection with *Pseudomonas aeruginosa* within 2 years prior to screening (Positive, Negative)

In addition, data listings will also be provided for:

- Informed consent;
- Inclusion/Exclusion criteria violation for subjects with any such violations.

